7. STUDY PROCEDURES

7.1 Schedule of Assessments

Eligible subjects who have signed the ICF and meet the inclusion/exclusion criteria requirements for this FOURIER OLE study will be enrolled at the completion of the FOURIER study. Subject identification numbers will be the same as those in FOURIER. Assessments done for the FOURIER/EBBINGHAUS (as applicable) EOS visit do not need to be repeated for this study, unless day 1 in this study (FOURIER OLE) occurs > 90 days after the FOURIER EOS visit. Baseline data for participating subjects will be carried over from the FOURIER study.

Approved

Table 1. Schedule of Assessments

Time Point	Treatment Period (\pm 14 days)												Safety Follow-up
	Day 1 ^a	Wk12	Wk24	Wk48	Wk72	Wk96	Wk120	Wk144	Wk168	Wk192	Wk216	Wk240 ^b	Wk260
GENERAL AND SAFETY ASSESSMENTS													
Informed consent	X												
Targeted concomitant therapy	X ^d	X	X	X	X	X	X	X	X	X	X	X	X
Adverse events	X	X	X	X	X	X	X	X	X	X	X	X	X
Device-related adverse effects	X	X	X	X	X	X	X	X	X	X	X	X	X
Serious adverse events	X	X	X	X	X	X	X	X	X	X	X	X	X
Disease-related events	X	X	X	X	X	X	X	X	X	X	X	X	X
Physical examination	X ^d												X
Vital signs ^e	X ^d	X	X	X	X	X	X	X	X	X	X		X
Body weight	X ^d	X	X	X	X	X	X	X	X	X	X		X
Coronary revascularization procedure and death information ^f	X	X	X	X	X	X	X	X	X	X	X	X	X
NEUROCOGNITIVE ASSESSMENTS													
CANTAB SWM test ^g	X ^d		X		X		X		X				X
CANTAB PAL test ^g	X ^d		X		X		X		X				X
CANTAB RTI test ^g	X ^d		X		X		X		X				X
LABORATORY ASSESSMENTS^h													
Fasting lipid panel	X ^d	X	X	X	X	X	X	X	X	X	X		X
ApoA1, ApoB, Lp(a)	X ^d	X	X	X	X	X	X	X	X	X	X		X
Pregnancy test ⁱ	X	X	X	X	X	X	X	X	X	X	X		X
FSH ^j	X												
DOSING													
Administration at study site ^k	X	X	X	X	X	X	X	X	X	X	X	X	X
Dispense/reconcile evolocumab ^l	X	X	X	X	X	X	X	X	X	X	X	X	X

Footnotes defined on next page of the table

Approved

ApoA1 = apolipoprotein A1; ApoB = apolipoprotein B; CANTAB = Cambridge Neuropsychological Test Automated Battery; **eCRF = electronic case report form**; EOS = end of study; FSH = follicle-stimulating hormone; Lp(a) = lipoprotein(a); PAL = Paired Associates Learning; Q2W = every 2 weeks; QM = monthly; RTI = Reaction Time; SWM = Spatial Working Memory; Wk = week

Mandatory study visits will occur at week 12 and thereafter approximately every 24 weeks from day 1. Resupply visits will be scheduled quarterly (every 12 weeks).

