- review of targeted concomitant therapy
- review of adverse events, serious adverse events, device-related adverse effects, and disease-related events. Any events that occurred between FOURIER EOS and day 1, if applicable, will be recorded on the Event eCRF.
- physical examination
- vital signs (sitting blood pressure and heart rate)
- body weight
- **coronary revascularization procedure and death information (sites will be prompted for this information when necessary)**
- CANTAB SWM, PAL, and RTI tests (subjects who participated in the EBBINGHAUS study only)
- blood draws for fasting lipids (\geq 9-hour fasting sample), ApoA1, ApoB, Lp(a), and FSH (only if required to ensure menopause [see [Exclusion Criterion 207](#)])
- blood draw or urine sample for a serum or urine pregnancy test (women of childbearing potential only)
- administration of evolocumab at study site (see [Section 6.2.1](#) for instruction and supervision of subjects), if applicable
- dispensing evolocumab (prefilled AI/Pens or PIs), if applicable

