9.2.2 Adverse Events

9.2.2.1 Reporting Procedures for Adverse Events That Do Not Meet Serious Criteria

The investigator is responsible for ensuring that all adverse events observed by the investigator or reported by the subject that occur after the FOURIER EOS visit through the EOS visit for this OLE study, or 30 days (+ 3 days) after the last administration of evolocumab, whichever is later, are reported using the Event eCRF. The investigator is responsible for ensuring that all device-related adverse effects observed by the investigator or reported by the subject that occur after the FOURIER EOS visit through the EOS visit for this OLE study or 30 days (+ 3 days) after the last administration of evolocumab, whichever is later, are reported using the Event eCRF.

The investigator must assign all of the following adverse event attributes:

- adverse event diagnosis or syndrome(s), if known (if not known, signs or symptoms)
- dates of onset and resolution (if resolved)
- severity
- assessment of relatedness to investigational product (evolocumab and/or the medical devices [prefilled AI/Pen or PI]), any study-mandated activity or procedure, or other protocol-required/study-mandated therapies
- action taken

The adverse event grading scale used will be the CTCAE. The grading scale used in this study is described in [Appendix A](#). If the severity of an adverse event changes from the date of onset to the date of resolution, record as a single event with the worst severity on the Event eCRF.

The investigator must assess whether the adverse event is possibly related to investigational medicinal product (evolocumab). This relationship is indicated by a “yes” or “no” response to the question: Is there a reasonable possibility that the event may have been caused by the investigational medicinal product?

The investigator must assess whether the adverse event is possibly related to the prefilled AI/Pen or PI investigational device used to administer investigational medicinal product (evolocumab). The relationship is indicated by a “yes” or “no” response to the question: Is there a reasonable possibility that the event may have been caused by the investigational device?

The investigator must assess whether the adverse event is possibly related to study-mandated statin background therapy. This relationship is indicated by a “yes” or

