5.1 Study Time Points

Baseline

The baseline value is defined as the subject's baseline value from the parent study, unless otherwise specified.

First Dose Date of Investigational Product (IP)

For each subject, the first dose date of IP is the date of the first administration of evolocumab in this OLE study.

End of Investigational Product (EOIP) Date

For each subject, end of investigational product is the date reported on End of Investigational Product Administration eCRF.

Last Dose Date of Investigational Product

For each subject, the last dose date of investigational product is defined as the date of the last administration of investigational product (evolocumab or placebo).

If the last dose was administered in-clinic, then the Last IP Dose Date is the last start date captured on the IP Administration (In-Clinic) eCRF page.

If the last dose was administered at a non-investigator site location, then the Last IP Dose Date is defined as the final dose date reported by the subject on the Non-Clinic Final Investigational Product Dose Date eCRF page.

End of Study (EOS) Date

For individual subject, the end of study date is defined as the last day that protocol-specified procedures are conducted for an individual subject, including safety follow-up and survival assessment. The EOS date is recorded on the End of Study eCRF.

Enrollment Date

The enrollment date for each subject is recorded on the Subject Enrollment eCRF **in the OLE study.**

Study Day 1

The date of the first administration of evolocumab in the OLE study or the **enrollment date** for subjects who are not administered any dose of evolocumab.

Study Day

For each subject, and for a given date of interest, study day is defined as the number of days since study day 1:

Study day = (date of interest – study day 1 date) + 1

If the date of interest is prior to the study day 1:

Study day = (date of interest – study day 1 date)

Study End Date

The study end date is the last EOS date of all enrolled subjects.

Endpoint Categories

All time-to-**first**-event endpoints in this study are categorized below.

- Composite
 - time to cardiovascular death, myocardial infarction, hospitalization for unstable angina, stroke, or coronary revascularization, whichever occurs first
 - time to cardiovascular death, myocardial infarction, or stroke, whichever occurs first
 - time to cardiovascular death or hospitalization for worsening heart failure, whichever occurs first

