For analyses based on OLE data only		
Composite or Non-mortality	First event onset date reviewed by CEC in OLE study – enrolment date in OLE study +1	EOS date in OLE study
Mortality	Death endpoint date reviewed by CEC in OLE study – enrolment date in OLE study +1	For subjects who died not due to death endpoint, the censoring date is the death date (reviewed by CEC) in OLE study For remaining subjects, the censoring date is max (EOS date, last known survival status date from eCRF page(s)) in the OLE study

Patient-years of follow-up for treatment emergent adverse events

For analyses based on combined both the parent study and this OLE study:

- 1) Subjects had events: date (first event) – date (first dose date in FOURIER) + 1
- 2) Subjects didn't have events: min [date (EOS in OLE), date (last dose date in OLE)+30] – date (first dose date in FOURIER) + 1

For analyses based on OLE study:

- 1) Subjects had events: date (first event in OLE) – date (first dose date in OLE) + 1
- 2) Subjects didn't have events: min [date (EOS in OLE), date (last dose date in OLE)+30] – date (first dose date in OLE) + 1

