5.3 Other Study Related Definitions

Treatment-Emergent Adverse Event (TEAE)

Events are categorized as Adverse Events (AEs) or **Disease-related Events (DREs)** starting on or after first dose of investigational product as determined by the flag indicating if the event started prior to the first dose on the Events eCRF and up to the EOS/Safety Follow-up visit or 30 days after the last administration of evolocumab, whichever is earlier.

Treatment-Emergent Disease-Related Events

Events categorized as Disease-related Events defined in Protocol Section 9.1.1 starting on or after first dose of investigational product as determined by the flag indicating if the disease-related event started prior to the first dose on the Events eCRF and up to the EOS/Safety Follow-up visit or 30 days after the last administration of evolocumab, whichever is earlier.

Analytical Study Week Assignments

Analytical windows will be used to assign parameters to study weeks. The algorithm is provided in Appendix A.

Investigational Product (IP)

Investigational product includes evolocumab 140 mg every two weeks (Q2W) and 420 mg monthly (QM).

IP Exposure Period in Months (For OLE period)

For subjects whose last IP dose is Q2W:

IP exposure period in OLE period= $[\min(\text{last IP dose date in OLE period} + 14 \text{ days, EOS date}) - \text{first IP dose date in OLE period} + 1] / 365.25 \times 12$

For subjects whose last IP dose is QM:

IP exposure period in OLE period= $[\min(\text{last IP dose date in OLE period} + 28 \text{ days, EOS date}) - \text{first IP dose date in OLE period} + 1] / 365.25 \times 12$

IP Exposure Period in Months (For combined the parent and OLE periods)

For subjects whose last IP dose is Q2W:

IP exposure period in combined periods= $[\min(\text{last IP dose date in OLE period} + 14 \text{ days, EOS date in OLE period}) - \text{first IP dose date in the parent period} + 1] / 365.25 \times 12$

For subjects whose last IP dose is QM:

IP exposure period in combined periods= $[\min(\text{last IP dose date in OLE period} + 28 \text{ days, EOS date in OLE period}) - \text{first IP dose date in the parent period} + 1] / 365.25 \times 12$

Study Exposure Period in Months (For OLE period)

For each subject, study exposure period in OLE period = $[(\text{EOS date} - \text{enrollment date}) + 1] / 365.25 \times 12$

Study Exposure Period in Months (For combined the parent and OLE periods)

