9.5.1 Analyses of Primary Endpoint

The current Medical Dictionary for Regulatory Activities version at the time of data lock will be used to code all adverse events (AEs) and disease related events to a system organ class and a preferred term.

Treatment-emergent adverse events are defined in [Section 5.3](#).

The subject incidence and exposure-adjusted subject incidence rate of all treatment-emergent adverse events, serious adverse events, fatal adverse events, adverse events leading to withdrawal of evolocumab, device-related adverse events, and disease-related events will be tabulated by system organ class (SOC), high level term (HLT), and preferred term (PT) in alphabetical order for the OLE only study period using the OLE safety analysis set. These events will also be presented by yearly subject exposure time intervals. All adverse event summaries for the primary analysis of the primary endpoint will include all treatment-emergent events reported on the Event eCRF, including CEC reviewed events and disease related events.

The analyses described above (subject incidence, exposure-adjusted subject incidence rate) will also be performed combining data from the OLE study and the parent study using the OLE safety analysis set and also be analyzed separately for the subgroup of subjects who were randomized to and received evolocumab group in the parent study with ≥ 7 years of the combined exposure for evolocumab across the **combined** parent and OLE **study**. Events from parent study classified as Target IP TEAEs will be included (adverse events occurring from the first dose of IP date to 30 days after the last dose of IP date or EOS, whichever occurs first). Disease-related events from the OLE study will be reclassified as adverse events and positively reviewed events from the OLE

study will not be included to remain consistent with parent study adverse event reporting. This analysis will be presented by the randomized treatment in the parent study.

Subject incidence of treatment emergent and serious adverse events occurring in at least 1% of the subjects by preferred term will be provided in descending order of frequency for the OLE **only** study period **and combined parent and OLE study periods.**

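### Combined FOURIER+OLE TEAE patient-years include between-study days on which almost no event can count, so combined exposure-adjusted rates are biased low wherever there is a gap

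*SAP*

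**What the plan says.** **Denominator.** In SAP 5.1, combined patient-years start at the first FOURIER dose. They run to the first event or, for event-free subjects, to the earlier of OLE end of study and last OLE dose plus 30 days: "date (last dose date in OLE)+30] – date (first dose date in FOURIER) + 1". Nothing is subtracted for time between the studies.

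**Numerator, FOURIER part.** SAP 9.5.1 takes parent-study events from first dose "to 30 days after the last dose of IP date or EOS, whichever occurs first".

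**Numerator, OLE part.** SAP 5.3 takes events "starting on or after first dose of investigational product as determined by the flag" on the Events eCRF. SAP 5.1 fixes that dose: "the first dose date of IP is the date of the first administration of evolocumab in this OLE study".

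**OLE-only formula.** For subjects with an event, SAP 5.1 uses "date (first event in OLE) – date (first dose date in OLE) + 1". It starts where the OLE event window opens.

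**Gaps.** Protocol 7.2 recommends that OLE day 1 fall on the day of the FOURIER end-of-study visit, and otherwise no later than 90 days after it. Protocol 7.1 also provides for longer gaps: assessments are not repeated "unless day 1 in this study (FOURIER OLE) occurs > 90 days after the FOURIER EOS visit".

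**Gap events.** Protocol 9.2.2.1 makes reportable the events that "occur after the FOURIER EOS visit through the EOS visit for this OLE study", and Protocol 7.2.1 adds: "Any events that occurred between FOURIER EOS and day 1, if applicable, will be recorded on the Event eCRF". SAP 9.7 plans a listing of events between FOURIER end of study and OLE enrolment.

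**The concern.** An exposure-adjusted incidence rate needs one risk window for both parts: person-time should accrue only while an event would be counted. The combined formula breaks this between the studies. Each subject who reaches the gap without a countable event adds person-time there and almost no possibility of an event. The error can only lower the rate.

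The affected tables are the combined long-term TEAE rates, including those for the subgroup with at least 7 years of evolocumab. In a study whose purpose is long-term safety, a one-directional downward error in the pooled rates should not be left in the definitions, even if it proves small.

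**Working it through.** The plan states no combined rate, gap distribution or subgroup count, so there is no figure to reproduce. The check compares the windows and then sizes the mismatch under stated assumptions.

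**1. Windows side by side**

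| Period | In denominator? | Dated event counted? |
|---|---|---|
| First FOURIER dose to min(FOURIER EOS, last FOURIER dose + 30) | Yes | Yes |
| After that, until first OLE dose | Yes, if no earlier countable event | No |
| First OLE dose to min(OLE EOS, last OLE dose + 30) | Yes, until first event | Yes |

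Three details follow.
- Gap days are also carried by subjects whose first counted event is in the OLE. Only those with a countable event in FOURIER escape.
- The 30-day tail does not bridge a short gap, because it is cut at FOURIER end of study. If the last FOURIER dose was more than 30 days before that visit, the uncounted stretch starts even earlier.
- There is one narrow exception. Under SAP 8.3.2, an event that cannot be placed before or after first dose is counted as treatment-emergent.

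**2. Size of the dilution**

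Inputs:
- T2 = 260 weeks = 1820/365.25 = 4.983 years (Protocol 3.5.1).
- Assumed: T1 = 2 years in FOURIER; constant hazard λ per year; uncounted gap of g years in a fraction f of subjects.

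Formulas, per subject:
- Matched person-time: P = [1 − exp(−λ(T1+T2))]/λ, which tends to 6.983 years for rare events.
- Extra person-time under SAP 5.1: E = f·g·exp(−λ·T1).
- The counted events are the same, so the relative shortfall of the rate is E/(P + E).

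Examples with 90 days for everyone (g = 90/365.25 = 0.2464):
- Rare event: 0.2464/(6.983 + 0.2464) = 3.4%.
- λ = 0.4: E = 0.2464 × exp(−0.8) = 0.1107 and P = 2.347, giving 0.1107/2.458 = 4.5%.

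| Assumed gap | Rare event | λ = 0.4 per year |
|---|---|---|
| Same-day rollover | 0 | 0 |
| 7 days, all subjects | 0.27% | 0.37% |
| 30 days, all subjects | 1.16% | 1.55% |
| 90 days, 25% of subjects | 0.87% | 1.17% |
| 90 days, all subjects | 3.4% | 4.5% |

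The shortfall peaks near λ = 0.4 and then falls: with 90 days for all it is 3.2% at 1 per year and 0.9% at 2 per year. It also depends on FOURIER time. For a rare event with 90 days for all it is 4.0% with T1 = 1 year and 3.0% with T1 = 3 years.

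**3. The 7-year subgroup, if SAP 5.3 combined IP exposure defines it**

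That formula also runs unbroken from first parent dose to last OLE dose plus 14 days (Q2W) or 28 days (QM). Seven years is 7 × 365.25 = 2556.75 days. OLE end of study is at least 30 days after the last dose (Protocol 7.2.3), so it does not cap the credit.

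| OLE completer | OLE exposure (days) | FOURIER days needed | Exactly 2 FOURIER years (730.5 days), no gap |
|---|---|---|---|
| QM, last dose at week 260 | 1821 + 28 = 1849 | 707.75 | in, by 22.75 |
| Q2W, last dose at week 260 | 1821 + 14 = 1835 | 721.75 | in, by 8.75 |
| Last dosing interval ends at week 260 | 1821 | 735.75 | out, by 5.25 |

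Suppose the same 14- or 28-day credit is allowed after the last FOURIER dose. Each gap day beyond it then lowers the FOURIER requirement by one day. In the third row, six such days bring the subject in.

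**The case against.** The case for leaving the plan alone is mainly about consequence. Protocol 7.2 asks for gaps to be minimised and recommends same-day rollover, where the effect is normally nil. The combined analysis is additional and descriptive, with no inference and no decision rule. Gap events are collected and listed. All of this stands and limits the importance of the point. It does not remove the mismatch: the protocol allows for gaps, and a listing cannot correct a rate.

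The objection is stronger on the subgroup. Neither SAP 4.2 nor 9.5.1 says which exposure formula sets the 7-year flag, and SAP 5.3 also defines a combined study exposure period. Protocol 2.3 builds its 7 years from the calendar span between the start of FOURIER and completion of the OLE. The IP formula does not subtract missed doses within either study. Two of the three margins above are smaller than the 14-day visit window, so ordinary visit timing can decide entry too. A reader might infer that the subgroup is wrongly defined. The documents do not support that: the concern applies only if the IP formula is the one used. That is the natural reading of exposure to evolocumab, but the SAP does not state it.

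A reader might also infer that the gap favours one randomised group. The formula is the same for both, and nothing in the documents suggests that gaps differ by group.

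**Conclusion.** The mismatch is real and follows from the SAP's own definitions. Combined FOURIER+OLE exposure-adjusted TEAE rates are biased low for every subject with an uncounted gap and no countable event in FOURIER, apart from the narrow exception for events of undeterminable timing.

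The size is unknown because the gap distribution is not given. With 2 FOURIER years plus 260 weeks, a constant hazard and rates up to about 0.4 per year, a plausible partial gap (a quarter of subjects at 90 days) costs about 1%. The 3.4% to 4.5% figure needs every subject at 90 days and should not be read as the expected effect. Same-day rollover gives zero, provided the last FOURIER dose was within 30 days of FOURIER end of study.

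A reader might extend this to the primary endpoint. That would be wrong: the OLE-only formula and its event window start on the same day, so the primary analysis is unaffected. The subgroup point is secondary and conditional on which formula sets the flag; the number of subjects near the cut-off is not known.

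**What to change.** In SAP 5.1, define combined TEAE person-time as the sum of two segments, with no day counted twice and truncated at the first countable event:
- first FOURIER dose to min(FOURIER EOS, last FOURIER dose + 30);
- first OLE dose to min(OLE EOS, last OLE dose + 30).

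Counting the collected gap events in the numerator would also align the two parts. It would bring off-treatment events into a treatment-emergent rate, so the two-segment definition is preferable.

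In SAP 4.2, name the formula that sets the 7-year flag. If it is the SAP 5.3 combined IP exposure, replace the unbroken span with the sum of the two dosing periods. End the FOURIER period at the earlier of last FOURIER dose plus 14 or 28 days and first OLE dose; leave the OLE period as now defined.

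The cost is SAP wording and minor programming, since the dates are already needed for the existing formulas and event windows. Where gaps exist, combined rates rise slightly, and a few subjects may leave the 7-year subgroup if its flag is changed. OLE-only results do not change.

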5.2 Demographic and Baseline-related Definitions

Age

Age is the subject's age at the parent study baseline. Age at enrollment is the subject's age in years as recorded on Demographics eCRF of the parent study.

Baseline Lipid and Lipid-related Parameters

Baseline values for lipids (total cholesterol, HDL-C, non-HDL-C, LDL-C, VLDL-C, and triglycerides), ApoA1, ApoB, hsCRP, Lp(a) and their derived parameters (eg, ratio between them) are defined as the mean of two most recent non-missing concentrations measured through central lab prior to or on the parent study randomization date. If for only reason only 1 value is available, then that value will be used as baseline.

Change (absolute change) From Baseline

The arithmetic difference from baseline for a given variable at a given time point:

Change from baseline = (value at given time point – baseline value)

Percent Change From Baseline

The percent change from baseline for a given variable at a given time point is defined as: $100 \times (\text{change from baseline} / \text{baseline value})$

Baseline Metabolic Syndrome

Baseline metabolic syndrome is defined as the history of metabolic syndrome at parent study baseline.

Baseline Major Risk Factors

Baseline major risk factors are defined at parent study baseline:

- Diabetes (type 1 or type 2)
- Age ≥ 65 years at randomization in parent study (and ≤ 85 years at time of informed consent in parent study)
- MI or non-hemorrhagic stroke within 6 months of screening in parent study
- Additional diagnosis of myocardial infarction or non-hemorrhagic stroke excluding qualifying MI or non-hemorrhagic stroke
- Current daily cigarette smoking
- History of symptomatic PAD (intermittent claudication with ABI < 0.85 , or peripheral arterial revascularization procedure, or amputation due to atherosclerotic disease) if eligible by MI or stroke history

Baseline Minor Risk Factors

Baseline minor risk factors are defined at parent study baseline:

- History of non-MI related coronary revascularization

- Residual coronary artery disease with $\geq 40\%$ stenosis in ≥ 2 large vessels
- Most recent HDL-C < 40 mg/dL (1.0 mmol/L) for men and < 50 mg/dL (1.3 mmol/L) for women by central laboratory before randomization
- Most recent hsCRP > 2.0 mg/L by central laboratory before randomization
- Most recent LDL-C ≥ 130 mg/dL (3.4 mmol/L) or non-HDL-C ≥ 160 mg/dL (4.1 mmol/L) by central laboratory before randomization
- Metabolic syndrome

Other Baseline Values

Other baseline values are defined at parent study baseline.

For targeted concomitant medications data, the medication taken at baseline is defined as the medication collected at day 1 visit (ie, currently medications taken at time of day 1 visit) in parent study.

For all other variables, the baseline value is defined as the last non-missing value collected prior to or on randomization date in parent study.

